Risks	
 - Radiation exposure is the main risk of this product - The radioactive element used in this product is ⁶⁸Ga and its dose is about 5 mCi. - Although SNA002 is a nano-molecule with extremely low immunogenicity, clinical trial observations are still needed to ascertain its potential risks. 	
 - The risk of radiation exposure is small and within the acceptable range.

Conclusion: The main risk (primarily radiation exposure) of the SNA002-based PET imaging diagnostic method is low. This method can noninvasively detect and evaluate PD-1 and PD-L1 expression in tumors, identify the temporospatial heterogeneity in tumors, simplify the complexity and reduce the time and cost of IHC detection, effectively improve the diagnosis and detection rates of tumor, provide new strategies for positive patient screening, treatment regimen optimization, and prognosis evaluation, and bring new insights to the clinical diagnosis and treatment of cancer.

3 Objectives and Purpose

Primary objectives

- To evaluate the safety and tolerability of single doses of SNA002 administered intravenously in patients with solid tumors
- To assess the biodistribution of SNA002 in patients with solid tumors

Secondary objectives

- To assess the radiation dosimetry of SNA002 in patients with solid tumors
- To assess the radiation dose of SNA002 in the blood of patients with solid tumors
- To explore the PET imaging characteristics of SNA002 in patients with solid tumor
- To identify the optimal dose
- To identify optimal image timing window

Exploratory objectives

- To explore the correlation between SNA002 uptake in tumor lesions and PD-L1 expression as determined by immunohistochemistry.
- To explore the positive and negative predictive efficacy of [⁶⁸Ga] Ga-NOTA-SNA002.

4 Study Design and Endpoints

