6.1.7 Starting Dose and Dose Escalation Schedule

6.1.7.1 Starting Dose

SNA002 does not bind to mouse, rat and dog PD-L1. Therefore, cynomolgus monkey was chosen in biodistribution studies and repeat-dose general toxicity studies. ^{68}Ga -NOTA-SNA002 can specifically bind to PD-L1 proteins of primates, and the radioactivity uptake is low in other organs except for the excretion organs (kidneys and bladder). The estimated absorbed dose (effective dose) converted from cynomolgus monkeys to adult male or female is 0.022-0.023mSv/MBq, which shows good radiation safety. The recommended dose of ^{68}Ga -NOTA-SNA002 for clinical trials is 185 MBq (5mCi), which generates an effective dose of about 4.1 mSv indicating safe use of ^{68}Ga -NOTA-SNA002 for clinical diagnostics. A NOAEL approach based on the pivotal monkey 2-week study toxicity findings was used to determine the maximum recommended starting dose (MRSD) for the first in human study. In the 2-week monkey study, the potential infusion reaction is the only toxicity observed after 3 repeated iv doses. the dose of 1.5 mg/kg (mean $\text{AUC}_{0-t} = 20700 \text{ ng}\cdot\text{h}/\text{mL}$; mean $\text{C}_{\text{max}} = 32000 \text{ ng}/\text{mL}$) and 0.5mg/kg (mean $\text{AUC}_{0-t} = 5060 \text{ ng}\cdot\text{h}/\text{mL}$; mean $\text{C}_{\text{max}} = 10500 \text{ ng}/\text{mL}$) was considered the NOAEL for males and females, respectively. Since the molecular weight of ^{68}Ga -NOTA-SNA002 is less than 100KD, The HED is 0.48 mg/kg (male) and 0.16 mg/kg (female) based on body surface. The MRSD is considered to be 0.048 mg/kg (male) and 0.016 mg/kg (female) (1/10 of NOAEL). The highest dose that nonclinical can cover is considered to be 0.24 mg/kg (male) and 0.08 mg/kg (female) (1/2 of NOAEL). The proposed human dose ranges are from 0.00167 mg/kg (0.1mg flat dose) starting dose to the highest ascending dose 0.01503mg/kg (0.9mg flat dose). The starting dose is 28.74- and 9.58-fold lower than the MRSD for males and females, respectively. The highest ascending 0.01503 mg/kg is covered by nonclinical data ($\frac{1}{2}$ of the NOAEL). Therefore, the proposed clinical mass dose range of 0.00167mg/kg to 0.01503mg/kg is not expected to pose a significant risk to patient safety.

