6.1.10 Tracking of Dose

SNA002 will only be intravenously injected once in the trial.

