8.2.2 RELATIONSHIP TO STUDY AGENT

Correlation determination can be done using the five point method: relevant, highly likely related, possibly related, possibly unrelated, or unrelated. Dichotomy can also be used: relevant or unrelated (those that are relevant, highly likely related, or possibly related can be classified as "relevant" according to the dichotomy method; those that are unrelated or potentially unrelated can be classified as "unrelated" according to the dichotomy method).

Table 5 Classification and criteria for determining the correlation between adverse events in clinical drug trials

Five point method	Basis of determination	Dichotomy
Related	
 - Has a reasonable temporal relationship -Conforming to known drug mechanisms, characteristics, or known adverse reactions -De-excitation positive -No other plausible explanation -Re-excitation positive 	relevant
Probably	- Has a reasonable temporal relationship	

Related	
 -Conforming to known drug mechanisms, characteristics, or known adverse reactions -De-excitation positive -No other plausible explanation -Absence of Re-excitation positive proof. 	
Possibly Related	
 -Has a reasonable temporal relationship -Absence of re-excitation positive proof -Manifested as any of the following situations: 
 ①Conforming to known drug mechanisms, characteristics, or known adverse reactions, de-excitation positive, but other reasonable reasons can also be used for explanation. ② Conforming to known drug mechanisms, characteristics, or known adverse reactions, absence of de-excitation positive proof, and there are no other reasonable reasons to explain. ③Does not conform to the known mechanism of action, properties or known adverse reactions of the drug, de-excitation positive, and there is no other reasonable reason to explain. ④ Does not conform to the known mechanism of action, properties or known adverse reactions of the drug, de-excitation positive,also explained by other plausible reasons. ⑤ Does not conform to the known mechanism of action, , properties or known adverse reactions of the drug,absence of de-excitation positive proof, and no other plausible reason to explain. 	

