8.5 Study Halting Rules

Administration of study agent will be halted when three grade 2 AEs determined to be “probably related” are reported to the IRC. The IRC will notify the study sponsor and investigators immediately when the third grade 2 event is reported, and enrollment screens will stop accepting new study participants.

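### On the five-point causality scale, the section 8.5 halt cannot count a grade 2 reaction outside the drug's known profile, even when timing fits and nothing else explains it

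*Combined protocol and SAP*

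**What the plan says.** Section 8.5 reads "Administration of study agent will be halted when three grade 2 AEs determined to be" probably related and reported to the IRC; enrolment then stops.

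Table 5 in section 8.2.2 defines the causality classes. Related and Probably Related both list this criterion: "Conforming to known drug mechanisms, characteristics, or known adverse reactions". Both also need reasonable timing, positive de-excitation (taken here to mean dechallenge) and no other plausible explanation. Related further needs a positive rechallenge.

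Possibly Related has five situations. Two concern an event that does not fit the known profile and has no other explanation. Situation 3 ends "properties or known adverse reactions of the drug, de-excitation positive, and there is no other reasonable reason to explain". Situation 5 ends "absence of de-excitation positive proof, and no other plausible reason to explain". Section 8.2.2 also permits a two-point scale, relevant or unrelated.

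The known profile is thin. Section 6.1.7.1 derives a "maximum recommended starting dose (MRSD) for the first in human study", and in the two-week monkey study "the potential infusion reaction is the only toxicity observed after 3 repeated iv doses". Table 3 in section 2.2 adds that "clinical trial observations are still needed to ascertain its potential risks". Section 6.1.10 states that "SNA002 will only be intravenously injected once in the trial".

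Two other fixed rules use grade 2 events. Section 6.1.7.2 stops escalation when at least half of a dose group has adverse reactions of grade 2 or above. Section 5.4 terminates the trial when over half of the subjects have drug-related events of grade 2 or above.

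**The concern.** A halting rule in a first-in-human study should respond to reactions that nobody predicted. Section 8.5 borrows a causality class that depends partly on what is already known about the drug. A reaction can therefore fall outside the count because its type is unfamiliar, although the evidence that the drug caused it may be no weaker.

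Participant protection is at stake, not an endpoint: section 8.3 documents all adverse events regardless of relationship. Section 8.5 is the only fixed rule that stops dosing on a count of non-serious grade 2 reactions below one half. Under that level, non-conforming reactions are left to the judgement of the principal investigator, the sponsor and the safety committee.

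**Working it through.** **Step 1: classify an unexplained grade 2 event.** Take an event with reasonable timing, no other reasonable explanation and no rechallenge (one injection per subject, section 6.1.10). The first three columns are Table 5; the last is section 8.5.

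| Fits known profile? | Dechallenge shown? | Table 5 class | Counted by 8.5? |
|---|---|---|---|
| Yes | Yes | Probably Related | Yes |
| Yes | No | Possibly Related, situation 2 | No |
| No | Yes | Possibly Related, situation 3 | No |
| No | No | Possibly Related, situation 5 | No |

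Related is no way round, because it needs both conformity and a positive rechallenge. Non-conforming events are excluded in both of their rows, so that result does not depend on how dechallenge is read after one injection. The contrast with conforming events does depend on it. If abatement counts as dechallenge, a conforming event with the same course is counted. If not, conforming events are situation 2 and section 8.5 can count almost nothing.

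**Step 2: the two-point scale.** It has no probable level, so section 8.5 gives no rule for counting.

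**Step 3: how many such reactions can pass the other rules?** Inputs: four dose groups of 3 to 7 (section 10.5), 4 × 3 = 12 and 4 × 7 = 28. The reactions are non-serious and grade 2, so the serious-event and grade 3 rules do not apply. Sections 5.4 and 6.1.7.2 are read as including possibly related events.

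- The largest k with k/n below 1/2 is 1 for n = 3 and 3 for n = 7.
- Checking after every subject does not lower this. Reactions in subjects 3, 5 and 7 of a group give 1/3, 2/5 and 3/7, all below 1/2.
- Over four groups: 4 × 1 = 4 of 12 (33%) and 4 × 3 = 12 of 28 (43%). Both are below one half overall, so section 5.4 is not met.

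**Step 4: illustrative probabilities.** The documents give no reaction rate for this drug. In two related tracers (sections 2.1.1 and 2.1.3), no drug-related event above mild was reported in 22 + 16 = 38 patients. The one-sided 95% upper limit is 1 − 0.05^(1/38) = 0.076. These are different molecules, so rates of 2%, 5% and 10% are assumptions. Let X be the number of subjects with an unexplained grade 2 reaction, X ~ Bin(N, p), with independent subjects and at most one such reaction each.

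| Quantity | N | p = 2% | 5% | 10% |
|---|---|---|---|---|
| P(X ≥ 3) | 12 | 0.002 | 0.020 | 0.111 |
| P(X ≥ 3) | 28 | 0.018 | 0.163 | 0.541 |
| P(8.5 halts), half non-conforming (rate p/2) | 12 | 0.0002 | 0.003 | 0.020 |
| P(8.5 halts), half non-conforming (rate p/2) | 28 | 0.003 | 0.032 | 0.163 |
| P(X ≥ 3, 6.1.7.2 not met), check at group end | 12 | 0.0007 | 0.009 | 0.045 |
| P(X ≥ 3, 6.1.7.2 not met), check at group end | 28 | 0.018 | 0.162 | 0.530 |
| P(X ≥ 3, 6.1.7.2 not met), check after every subject | 12 | <0.0001 | 0.0003 | 0.002 |
| P(X ≥ 3, 6.1.7.2 not met), check after every subject | 28 | 0.006 | 0.046 | 0.122 |

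The half-non-conforming rows read abatement as dechallenge; the one-half split is also assumed. If every such reaction is non-conforming, the chance that section 8.5 halts is 0. The last four rows enumerate all sequences within a group and convolve over four groups.

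**The case against.** The case against is substantial, and several parts of it stand.

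- **Known versus new.** A reader might infer that section 8.5 always counts a familiar reaction and ignores an identical unfamiliar one. The documents do not support that unconditionally. It holds only if abatement after a single injection counts as dechallenge, which they do not say.
- **New does not mean non-conforming.** A reader might infer that every previously unseen reaction is excluded. Table 5 asks for fit with mechanism, characteristics or known reactions, so a first hypersensitivity reaction to a protein could qualify. Infusion reactions are expected already.
- **The list can grow.** Table 5 does not limit known reactions to those known before the trial. The 12 of 28 figure needs either several different non-conforming types or one type still treated as not known after repeated occurrences.
- **Other explanations are common.** Subjects have cancer, may be under treatment and may be biopsied on day 2. Many events will fall in situations 1 or 4, uncounted before and after the fix.
- **Other safeguards exist.** Sections 8.1.3, 8.3 and 8.4.3 define unanticipated problems to include possibly related events, record them, and require immediate sponsor assessment of safety information. One drug-related serious event terminates the trial. A reader might infer that unexpected reactions go unwatched; they do not. But the unanticipated-problem process sets no stopping count.
- **Thresholds are a design choice.** Different causality thresholds in sections 5.4, 6.1.7.2 and 8.5 are not in themselves an error. Requiring a probable relation for a low absolute count is a reasonable guard against false halts.

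The last argument does not fully answer the point. The conformity criterion selects by prior knowledge of the reaction type, whereas a guard against false halts should screen out events with another explanation.

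**Conclusion.** The point holds, within limits. On the five-point scale, section 8.5 cannot count a grade 2 reaction outside the drug's known mechanism, characteristics or known reactions, however good the timing and however clearly other causes are excluded. On the two-point scale the rule is undefined.

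The ceiling is 4 of 12 or 12 of 28 subjects with such reactions and no fixed rule firing, provided the types are still treated as not known. That is a bound, not a forecast. At an assumed 2% rate, three or more unexplained grade 2 reactions are unlikely (0.002 at N = 12, 0.018 at N = 28). The larger figures rest on a 10% rate, above the 7.6% limit from the related tracers, and on four full groups, which the imaging rules may not produce.

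The defect is in which events are counted. It bears modestly on participant protection and alters no endpoint.

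**What to change.** In section 8.5, count grade 2 adverse events that have a reasonable time relation to the injection and no other reasonable explanation, whatever the reaction type, dechallenge status or causality scale. On the five-point scale these are Related, Probably Related, and Possibly Related situations 2, 3 and 5. Keep the count at three. Situations 1 and 4, which have another explanation, stay uncounted. Record on the adverse event form whether another reasonable explanation exists, so that the rule also works on the two-point scale. The meaning of dechallenge after one injection then no longer affects the halt.

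The cost is one sentence and one form field, with no extra visits or patients. A halt becomes somewhat more likely, only through reactions with no other explanation. At N = 28, with half of the reactions non-conforming and abatement read as dechallenge, the chance of a halt rises from 0.032 to 0.163 at an assumed 5% rate and from 0.163 to 0.541 at 10%. If abatement is not accepted as dechallenge, the rise is from near zero to the same 0.163 and 0.541.

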8.6 Safety Oversight

Safety oversight will be under the direction of a safety committee, composed of individuals with the appropriate expertise, including nuclear medicine expertise, pharmacologist.

9 Clinical Monitoring

9.1 Quality control and quality assurance

- Quality control measures of the laboratory: The laboratory should provide documents such as quality control certificate.
- Investigators participating in the clinical trial must have the professional skills, qualifications, and competence related to clinical trials. They must pass the qualification examinations. Minimum mobility of the investigators is required during the clinical trial.
- Before the clinical trial, the staff participating in the clinical trial should receive training on the protocol, current GCP, and SOP related to the present clinical trial.
- The study site should designate 1-2 imaging instruments for use in the clinical trial. The selected instruments must have a good performance and can completely satisfy the

requirements of the trial. The designated instruments should be attached with relevant certification documents.

- The operating staff of the instruments should be authorized by PI and the authorization remains valid during the clinical trial. Moreover, they should be familiar with the protocol and the standard operating procedure of the imaging instruments.
- The specific procedure and parameters of imaging can be found in the standard operating procedure.
- The drug preparation staff should have the qualifications for radioactive drug preparation. They should be authorized by PI, and the authorization remains valid during the clinical trial.

9.2 Monitoring

The CRA of sponsor will visit the study sites and perform clinical monitoring according to *Good Clinical Practice* and the Project Management Plan. The investigators should proactively cooperate with the CRA. The specific duties of CRA include the following:

- Before the clinical trial, the CRA should confirm that the clinical trial institutions are fully equipped and eligible in the following aspects: staff preparation and training, laboratory tests related to the trial, equipment and their working status, a sufficient sample size, and familiarity with the protocol requirements of the study participants.
- During the clinical trial, the CRA should focus on the implementation of the clinical trial protocol and confirm that ICF has been obtained from all subjects before the screening. The CRA should know of the enrollment rate and the progress of the clinical trial and confirm that the enrolled subjects are eligible.
- The CRA should confirm that all data records and reports are accurate and complete. All eCRFs are correctly input and consistent with the raw data. The CRA should also ensure that all mistakes or omissions are corrected or marked, with investigators' signature and date. The CRA should confirm that the dose modification, therapy change, concomitant medications, loss to follow-up, and omissions in examinations are recorded for each subject. The CRA should confirm that the withdrawal and loss to follow-up are explained in the CRF for each enrolled subject.
- The CRA should confirm that all AEs are recorded and SAEs are reported and recorded within the stipulated time.
- The CRA should confirm whether the investigational drugs are supplied, stored, distributed, and recovered as per relevant laws and regulations and whether the corresponding records are kept.

- The CRA should record clearly and authentically any follow-up visits, tests or examinations that are not conducted by the investigators as required and any mistakes and omissions that are not corrected.
- The CRA should finish the monitoring report after each visit and report the problems to the investigators. The subjects are followed up until symptom disappearance or recovery to the baseline (or even better than the baseline), or disease stability, or the recovery of any laboratory abnormalities to normal or the baseline level, or loss to follow-up.
- During each follow-up, the CRA should check the PET/CT parameters and pay attention to the quality of the imaging instruments and the images.

9.3 Audit and inspection

Upon receiving the notice for audit and inspection, the investigators should inform the sponsor as soon as possible. The source documents of this clinical trial should be available for view by the sponsor's qualified staff or the designated personnel, or the inspector dispatched by the health and drug administration authorities. The above-mentioned personnel may need to verify the CRF or the data in EDC by directly browsing the source documents.

10 Statistical Considerations

10.1 Statistical and Analytical Plans

A formal SAP of this study will be completed prior to database lock and unblinding of the study data.

10.2 Statistical Hypotheses

This clinical trial is an exploratory study, and no hypothesis testing is set up.

10.3 Analysis Datasets

Full analysis set (FAS): Based on the intention-to-treat (ITT) principle, it includes all subjects who are enrolled after passing the screening.

Safety set (SS): It includes all subjects who receive the investigational drug (including the discontinuation after the initial administration) and have at least one safety observation record.

PK Dataset (PKS): All subjects who received the study drug and had at least one blood drug concentration data during the trial period.

10.4 Description of Statistical Methods

10.4.1 General Approach

This study mainly uses descriptive statistics.

In general, measurement data are described in mean, standard deviation, median, quartile, minimum, and maximum. Count data are described in frequency and percentage.

Unless otherwise stated, α is set to 0.05 (two-sided) for type I errors, and β to 0.2 for type II errors. All statistical tests are two-sided. $P \leq 0.05$ is taken to indicate significant difference.

10.4.2 Analysis of The Primary Efficacy Endpoints

Pharmacokinetic evaluation

- Change in whole blood radiation dose: Blood samples are collected on D1 after administration and the ^{68}Ga dose in blood samples is measured using a radiation detector.
- Change in serum radiation dose: Blood samples are collected on D1 after administration and the whole blood samples are treated to obtain serum. The ^{68}Ga dose in serum is measured using a radiation detector.
- SNA002 detection: Blood samples are collected on D1 after administration for the detection of SNA002 in blood samples in the central laboratory.
- Hemodynamic change of SNA002: Imaging results are interpreted and the heart is delineated as ROI. Data collected at various time points are analyzed, and the result is determined according to the concentration–time curve.
- Change in urine sample radiation dose: Urine samples should be collected before and post administration. ^{68}Ga dose in urine sample should be measured with γ detector.

Evaluation of imaging features

- Evaluation of PET imaging features of target tumor tissues: In combination with CT, the image results were read, multiple target tumor lesions were selected (no less than 1, ideally, no less than 1 should be selected for both positive and negative imaging foci), the uptake of $[^{68}\text{Ga}]$ Ga-NOTA-SNA002 in each target tumor lesion was observed, and the count was recorded, quantization for SUV-based standardized uptake (SUV_{max}, SUV_{mean} etc.).
- Tumor lesion hot spots by PET imaging——target to background ratio: Hot spot and T/B ratio is determined based on the SUV_{mean} (semi-quantitative analysis) of the target lesion and the lesion contralateral side and liver.
- Evaluation of optimal imaging time: The optimal imaging time is determined based on the T/B ratios at different time points.
- Optimal dosage: should be determined according to T/B ratio, detection ability of lesions (primary lesions, metastatic lymph nodes and distant metastases) and normal organs with abundant PD-L1 expression except lesions are fully inhibited.

